Continuous ratings that are collected at only one interval per device will be examined using either a paired t-test or the non-parametric Wilcoxon Signed-Ranks test, depending on the distribution of the paired differences. Mixed Models with repeated measures may be used for endpoints collected at multiple intervals per device.

Categorical ratings that are provided for each device will be analyzed using the McNemar test; if there are more than two levels for these ratings, they will need to be grouped into two levels for this analysis.

Categorical preference endpoints that are answered at the final visit (e.g., “Which device do you prefer?”) will be analyzed with a One-sample Binomial Test that compares the observed proportion to a 50/50 split.

Treatment Compliance and Missing Data

Any discontinued participants or protocol deviations will be tracked and reported in data listings. If a participant discontinues a device after the 15-day assessment, their ratings will be carried forward to the 30-day interval for the intent-to-treat analysis. This imputation will only be necessary for participants that complete at least the 15-day assessment for both devices. If a participant discontinues before providing ratings for both devices, they will be excluded from the analysis.

Safety Analysis

Safety evaluations will be performed by recording clinical adverse events at the time originally reported, and they will be followed at regular intervals until resolution, or until the study is completed, whichever comes first. Adverse events will be provided in data listings.

Interim Analysis

Preliminary results will be assessed after 10 participants complete the study, but the sample size will not be adjusted based on these interim outcomes.

Direct Access to Source Data/Documents

Only site clinical study staff and approved Philips staff working with the research will know the identity of the participants. All information recorded by the study team and provided for analysis will be given a study ID number. A unique source record will be created for each study participant.

Privacy rules and requirements according to federal and state governing regulations will be implemented. Except when required by law, participants will not be identified by name, social security number, address, telephone number, or any other direct personal identifier in study records. For records disclosed outside the Institution conducting this study, participants will be assigned a unique code number. The key to the code will be kept by the investigators. Data will be managed by study number and analyzed anonymously. The study record will include documentation of the informed consent form review process, HIPAA completion according to site policies, and applicable medical history. The Sponsor will have access to these source records.

In addition, participants' records including sensitive information and/or identifying information, may be inspected by the IRB, government agencies, and/or competent authorities, in the course of carrying out their duties.

All data will be kept confidential and in a secure location if on paper or on a secure server or device. Only approved study personnel will have access to study related documents. Approved study personnel are trained on privacy, HIPAA and data protection laws.

In addition, participant records may be reviewed in order to meet federal and state regulations. Reviewers may include representatives from the FDA or similar government authorities in other countries where the device is being used, and Philips Respironics for the purposes of the following side effects, and to gather additional information related to the study, and the IRB. Participant permission for review of confidential information is granted by signing the associated informed consent. Philips Respironics will ensure that it follows all applicable state and federal data protection regulations.

Data may be reviewed by any Philips research team, in any location, for purposes as outlined above, made available via a secure Philips site.

Case Report Forms

Study related eCRFs and source documentation will be collected and maintained by the sponsor, will be kept confidential, and stored in a secure location if on paper or on a secure server or protected device. Only staff delegated by the PI will have the ability to enter in, or make changes to, the eCRFs and source documents.

Quality Control and Quality Assurance

Each clinical site will perform internal quality management of study conduct, data collection, documentation and completion.

Quality control (QC) procedures will be implemented beginning with the data entry system and data QC checks that will be run on the database will be generated. Any missing data or data anomalies will be communicated to the site(s) for clarification/resolution.

The clinical monitor(s) will verify that the clinical trial is conducted and data are generated, tests are completed and documented (recorded), and reported in compliance with the

protocol and ICH GCP. Monitoring will be completed in accordance with FDA US CFR and ICH-E6 GCP Section 6, as applicable.

The investigational site will provide direct access to all source data/documents, and reports for the purpose of monitoring and auditing by the sponsor, and inspection by local and regulatory authorities.

Ethics

This study will be submitted and reviewed by an IRB. All participants will be consented prior to completing the trial. The Primary Investigator will review all AEs as it relates to the study device.

All the information collected as part of this study will be kept confidential. All information collected for this study will be kept in a secured area or stored in a password protected computer, if digital. Results of the study-related tests, medical history and information obtained from the questionnaires will be reported to the study sponsor (Philips Respironics, Inc.). Philips Respironics may use participant study data for research or regulatory purposes. Investigators may use participant study data to prepare research publications or presentations at meetings. No personally identifiable information will be used in any reports, meeting presentations, or publications of this study.

Data Handling and Recordkeeping

Hard copies of the study will be kept on site for at least 2 years after study completion. The sponsor will maintain study records indefinitely. Records will be stored at Iron Mountain, a secure information management services company.

Financing and Insurance

If the participant is injured during the course of the trial and as a direct result of this trial, they should contact the Principal Investigator. The participant will be directed to seek clinically appropriate medical care for that injury. However, we cannot guarantee that the medical care and treatment will be provided without charge or that it will be paid for by the participants insurance company, and the costs incurred may ultimately be the participant's responsibility.

Registration on ClinicalTrials.gov or other applicable registry

This trial will be registered at ClinicalTrials.gov, and results information from this trial will be submitted to ClinicalTrials.gov. In addition, every attempt will be made to publish results in peer-reviewed journals.

Risk and Benefit Analysis

Potential Risks and Discomforts

Adverse effects of nebulizer use are usually minor and manageable. All AEs encountered, will be recorded on data sheets that are part of the eCRF.

The risks of using the InnoSpire Go device are minimal. Use of nebulizer devices themselves do not have any known side effects. Side effects are generally associated with the medication being nebulized. The medications used in this study will be albuterol sulfate and combination ipratropium bromide/albuterol sulfate, which is a commonly prescribed medication for COPD patients.

Reported side effects of albuterol sulfate or combination ipratropium bromide/albuterol sulfate include tremors, dizziness, nervousness, headache, insomnia, nasal congestion, tachycardia, hypertension, bronchospasm, cough, bronchitis, wheezing, chest or body pain, diarrhea, dyspepsia, nausea, muscle cramps, bronchitis, lung disease, pharyngitis, pneumonia, urinary tract infection, constipation and voice alterations.^{20, 21}

The use of albuterol sulfate and ipratropium bromide singly or in combination has also been associated with precipitation or worsening of narrow-angle glaucoma, acute eye pain, blurred vision, mydriasis, exacerbation of COPD symptoms, drowsiness, aching, flushing, upper respiratory tract infection, palpitations, taste perversion, sinusitis, back pain, urticaria, angioedema, rash, oropharyngeal edema, arrhythmias (including atrial fibrillations, supraventricular tachycardia, extrasystoles) and metabolic acidosis.^{20, 21}

There are minimal risks of using the device and should they occur during the course of the study, they will be recorded. Other more serious AEs are distinctly unusual in the outpatient setting but will be recorded if they occur. Serious adverse events and device-related AEs will be reported to the IRB per their policy. Patients may find InnoSpire Go to be less comfortable than their previous nebulizer, but this is not a real medical risk.

Thus, we believe that although there may be discomforts associated with the use of this device and study related procedures, the risks are minimal.

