If a participant requests to stop using the device it does not mean discontinuation from the study, and remaining study procedures should be completed as indicated by the study protocol unless the participant does not wish to return and complete the follow-up visits. If a clinically significant side effect is identified (including, but not limited to negative changes from baseline) after enrollment, the investigator or qualified designee will determine if any change in participant management is needed. Any new any unfavorable and unintended sign (including an abnormal laboratory finding), symptom, or disease temporally associated with the use of the investigational device, whether or not related to the investigational device will be reported as an AE. See Assessment of Safety section for additional definitions and AE management.

Treatment of Subjects

Intended Use

InnoSpire Go is intended to be used as a general purpose mesh nebulizer used to aerosolize commonly prescribed liquid inhalation drugs for respiratory disease in children and adults. It is to be used by, but not limited to, patients with asthma, COPD and cystic fibrosis.

Contraindications

InnoSpire Go is not be used by patients that are unconscious or not breathing spontaneously.

Monitoring

Remote monitoring will be conducted for this study. Data that is directly entered into EDC will not be verified. 100% of the remaining data will be verified among 10% of the study participants' records.

This study will be monitored in compliance with Code of Federal Regulations (CFR) for clinical research; namely, 21 CFR Parts 50, 54, 56 and 812 and others as applicable. The purpose of such monitoring is to ensure that the rights and wellbeing of trial participants are protected, that the reported trial data are accurate, complete, and verifiable, and that the conduct of the trial is in compliance with the currently approved protocol/amendment(s), with International Conference on Harmonisation (ICH) Good Clinical Practice (GCP), and with applicable regulatory requirement(s). Monitoring visits will be performed periodically and will be conduct by trained clinical research

professionals. The monitoring process includes initial subject qualifications, periodic contact with the subject, and a final review once the study is complete.

It has been determined that this study does not require a Data Safety Monitoring Board (DSMB).

Unscheduled Visits

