Unscheduled calls and/or visits will be documented in the participant study file upon occurrence. Participants may be asked to receive additional phone calls in order to evaluate a technical or device issue and on an as needed basis.

Assessment of Performance

Device performance will be assessed based on the endpoints described in the Study Objectives and Purpose section.

Assessment of Safety

Adverse Events

Adverse event means any untoward medical occurrence associated with the use of an intervention in humans, whether or not considered intervention-related.

An adverse device effect (ADE) is an AE related to the use of an investigational medical device.

Serious Adverse Events

An AE or suspected adverse reaction is considered "serious" if, in the view of either the investigator or sponsor, it results in any of the following outcomes: death, a life-threatening AE, inpatient hospitalization or prolongation of existing hospitalization, a persistent or significant incapacity or substantial disruption of the ability to conduct normal life functions, or a congenital anomaly/birth defect. Important medical events that may not result in death, be life-threatening, or require hospitalization may be considered serious when, based upon appropriate medical judgment, they may jeopardize the participant and may require medical or surgical intervention to prevent one of the outcomes listed in this definition. Examples of such medical events include allergic bronchospasm requiring intensive treatment in an emergency room or at home, blood dyscrasias or convulsions that do not result in inpatient hospitalization, or the development of drug dependency or drug abuse.

Unanticipated Serious Adverse Device Effect

A USADE is a serious ADE which by its nature, incidence, severity or outcome has not been identified in the current version of the risk analysis report.

Severity of Event

The following guidelines will be used to describe AE severity:

- **Mild** – Events require minimal or no treatment and do not interfere with the participant’s daily activities.
- **Moderate** – Events result in a low level of inconvenience or concern with the therapeutic measures. Moderate events may cause some interference with functioning.

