- **Severe** – Events interrupt a participant’s usual daily activity and may require systemic drug therapy or other treatment. Severe events are usually potentially life-threatening or incapacitating. Of note, the term “severe” does not necessarily equate to “serious”.

Relationship to Study Intervention

All AEs must have their relationship to study intervention assessed by the clinician who examines and evaluates the participant based on temporal relationship and his/her clinical judgement. The degree of certainty about causality will be graded using the categories below. In a clinical trial, the study product must always be suspect.

- **Related** – The AE is known to occur with the study intervention, there is a reasonable possibility that the study intervention caused the AE, or there is a temporal relationship between the study intervention and event. Reasonable possibility means that there is evidence to suggest a causal relationship between the study intervention and the AE.
- **Not Related** – There is not a reasonable possibility that the administration of the study intervention caused the event, there is no temporal relationship between the study intervention and event onset, or an alternate etiology has been established.

Adverse Event Assessment and Follow-Up

Adverse events will be collected on an ongoing basis following signing of informed consent. Detailed information regarding the event will be recorded on the appropriate form in the electronic case report form (eCRF), where the Investigator will determine the severity of the event, relationship to study product (assessed only by those with the training and authority to make a diagnosis), and time of resolution/stabilization of the event. Follow-up data to ascertain the existence of residual effects from the event will be obtained. Serious adverse events must be reported to the sponsor within 24 hours of discovering the occurrence of the SAE. The research staff is required to complete and submit the sponsor’s standard SAE form detailing the event. Reports should be directed to:

[name], BSN, OCN
Senior Clinical Research Associate
[name]
[name]
[contact]
[contact]

Serious Adverse Event and Unanticipated Adverse Device Effect Reporting

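### Do the overlapping definitions of Related and Not Related adverse events need to be rewritten?

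*Combined protocol and SAP*

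**What the plan says.** The section Relationship to Study Intervention (under Assessment of Safety) has the examining clinician grade every adverse event as Related or Not Related, "based on temporal relationship and his/her clinical judgement". It adds that the study product is always to be treated as suspect.

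- **Related** holds if the event is known to occur with the intervention, if a reasonable possibility of causation exists, "or there is a temporal relationship between the study intervention and event". A reasonable possibility is defined as evidence pointing to causation, so it is a separate ground from timing.
- **Not Related** holds if "There is not a reasonable possibility that the administration of the study intervention caused the event", or if "there is no temporal relationship between the study intervention and event onset, or an alternate etiology has been established".

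The label feeds two other definitions. Under Adverse Events, "An adverse device effect (ADE) is an AE related to the use of an investigational medical device". A USADE is a serious ADE that "has not been identified in the current version of the risk analysis report". USADE incidence is part of the exploratory safety endpoint.

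Two other places separate being recorded as an event from being related. Discontinuation of Study Intervention covers any new unfavourable finding: one "temporally associated with the use of the investigational device, whether or not related to the investigational device will be reported as an AE". The general definition reads "Adverse event means any untoward medical occurrence associated with the use of an intervention in humans, whether or not considered intervention-related".

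**The concern.** Both definitions are lists of alternatives, each sufficient alone, and they are not complements. If an event follows device use but nothing suggests that the device caused it, the timing ground makes it Related and the missing causal evidence makes it Not Related. The same happens when an alternate etiology is established for an event that followed use. Two clinicians could label the same facts differently, and both would be following the text.

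The timing ground also sits awkwardly beside Discontinuation of Study Intervention. There, temporal association is what brings an event into the record, whether or not it is related. If timing alone settled relatedness, that distinction would lose much of its force.

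At stake would be the ADE label, anything triggered by it, and the USADE count if such an event were serious and absent from the risk analysis report.

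**Working it through.** **Inputs.** Four yes/no facts from Relationship to Study Intervention: K, known to occur with the intervention; P, reasonable possibility; T, temporal relationship; A, alternate etiology established.

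**Definitions as written.** Related = K or P or T. Not Related = (not P) or (not T) or A.

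**All 2^4 = 16 combinations.**

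| Facts | Combinations | Definitions met |
|---|---|---|
| P and T, not A (K free) | 2 | Related only |
| none of K, P, T (A free) | 2 | Not Related only |
| T, not P (K and A free) | 4 | both |
| T, P and A (K free) | 2 | both |
| not T, with K or P or both (A free) | 3 × 2 = 6 | both |

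Both: 4 + 2 + 6 = 12 of 16. Neither: 0.

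**How far common sense narrows this.** Three conditions can be added, none of which is in the documents.

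1. K implies P. This removes 4 combinations, all of them double-labelled, and leaves 8 of 12 in both.
2. A excludes P. This removes 4 more, all double-labelled, and leaves 4 of 8.
3. P requires T. This removes 2 more, both double-labelled, and leaves 2 of 6.

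The last two have timing, no reasonable possibility, and either value of A. A clinician who reads the facts coherently is left with this one kind of event. These are counts of logical cases, not event rates, and the documents give no rate for such events.

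**Where the label leads.**

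- *SAE incidence and reporting.* Seriousness does not depend on relatedness. SAEs go to the sponsor within 24 hours. One combined form for SAEs and unanticipated device effects goes to sponsor and IRB within 10 working days. No difference.
- *Adverse event listings* (Safety Analysis). All events are listed. No difference in what is included.
- *Primary endpoint.* This is the device preference question at Visit 5. No difference.
- *IRB reporting of non-serious events.* Potential Risks and Discomforts sends device-related events to the IRB under its policy. This can differ.
- *USADE count and the sponsor's evaluation of unanticipated effects.* These can differ, but only for a serious event missing from the risk analysis report. With 25 randomized, one such event gives 0/25 = 0% (exact 95% interval 0 to 13.7%) or 1/25 = 4% (0.1 to 20.4%). With 20 completers it gives 0% or 1/20 = 5%.

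**What a tighter rule would do.** Suppose Related required T, and (K or P), and not A, with all else Not Related. Of the 12 double-labelled combinations, only K, T, not P, not A becomes Related. The other 11 become Not Related. The overlap disappears, but non-serious events so relabelled leave the IRB route for device-related events. Letting Related prevail gives 12 + 2 = 14 of 16 Related and errs the other way.

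**The case for a change.** The strongest case for a change is that the contradiction is explicit and cheap to remove: one sentence in each definition plus the eCRF instructions. Neither clinical judgement nor the instruction to suspect the product is written as a precedence rule. The facts can also arise in ordinary use. Participants nebulize at least daily, so many events will follow a treatment, and the protocol says that side effects generally come from the medication rather than the device. A medication effect could then have timing and an alternate cause at once.

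The overlap stands, and so does the absence of a formal tie-breaker. Reading the Not Related list as joint conditions would clear the timing case, but the text uses alternatives.

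The conflict with Discontinuation of Study Intervention is weaker than it looks. That section governs what is recorded, while the other grades causality. Even if timing alone meant Related, Not Related would keep content. Events are collected from consent onwards, and participants assigned their own jet nebulizer first spend about 30 days without the InnoSpire Go. Events in that period have no temporal relationship to it.

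Cheapness does not decide the matter either. An edit must choose a side, and the choice is not neutral. Requiring causal evidence gives a more specific ADE label. Accepting timing alone is the more cautious reading and agrees with treating the product as suspect.

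**Conclusion.** The two definitions are not mutually exclusive, and that is a real imprecision in wording. It does not call for a change to the plan.

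The label is a clinician's judgement by design. It is assigned only by those trained and authorised to diagnose, with a stated basis and a stated direction of doubt, and the Ethics section has the principal investigator review all events in relation to the device. One label per event will result, and the eCRF records it with severity and resolution.

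The reach is small: the ADE label, IRB reporting of non-serious device-related events, and an exploratory USADE count that one disputed event would move by 4 percentage points among 25 participants. In a trial of this size any such event can be read individually in the listings, where it appears under either label. Serious events reach sponsor and IRB regardless.

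Whether timing alone should count as Related is a fair trade-off between caution and specificity, and it belongs to the sponsor and investigator.

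This conclusion assumes that clinicians use the definitions as guidance for judgement rather than as a mechanical test. It also rests on the documents giving no rate for such events. The risk analysis report, which decides whether a serious ADE is unanticipated, was not among the documents.
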